### **Clinicians: Across Both Conditions (i.e., Standardized and Tailored)**

#### **Phase 1 (Months 0-8)**

*Pre-Implementation.* The research team will recruit clinicians for participation via email and site visits. The study research assistants assigned to the Centerstone sites will follow-up with interested clinicians over the phone to provide additional information or answer any questions s/he may have about participating in the study.

#### **Phase 2 (Months 8 – 38)**

*5-Month Active Implementation.* Beginning at month eight, clinicians who provide individual psychotherapy to adults with depression (based on their self-reported typical and current caseload (i.e., clinicians will learn in the eligibility discussion that if they consent to participate in the study then they must have eligible clients to potentially enroll as well) and who conduct psychotherapy sessions in English will engage in the baseline mixed methods needs assessment. This assessment will consist of a battery of surveys and then, following the completion of these surveys a focus group will take place. Clinicians will be asked to complete the following baseline battery of self-reports (Appendix A): Demographic Questionnaire ([name] & Simons, 2011; Appendix A.1); Progress Monitoring Theory of Planned Behavior (Francis et al., 2004; Appendix A.2); Attitudes toward Standardized Assessment-Monitoring and Feedback (Jensen-Doss et al., *in press*; Appendix A.3); Monitoring and Feedback Attitudes Scale (Jensen-Doss et al., *in press*; Appendix A.4); Monitoring As Usual Measure (Lyon et al., 2015; A.5); Evidenced-Based Practices Attitudes Scale (Aarons, 2004; A.6); Survey of Organizational Functioning (Broome et al., 2007; A.7), Implementation Climate (Jacobs et al., 2014; A.8); Implementation Climate Scale (Earhart et al., 2014; A.9); Barriers and Facilitators to Implementing Survey (Salyers, Rollins, McGuire, & Gearhart, 2008; A.10); Sociometric Questionnaire (Valente et al., 2007; A.11); Opinion Leadership Scale (Childers, 1986) and self-nomination question (A.12); Implementation Leadership Scale (Aarons et al., 2014; A.13); and Perceptions of Adopting Measurement-Based Care (Moore & Benbasat, 1991; A.14). All questionnaires will be completed online using assessment software by emailing them a link or via hard copy (in-person). These questionnaires will take about 60 minutes to complete and clinicians who complete the baseline assessment will receive \$50 compensation. Using the data from these surveys, a subsample of clinicians at each site, selected using purposeful sampling for extreme variation (Palinkas et al., 2013), will be asked to participate in a 1.5 hour focus group (Appendix E.1). Clinicians who participate in the focus group(s) will receive \$25 compensation. Focus groups will be recorded and transcribed with data de-identified for the purposes of qualitative coding. Staff who do not provide individual psychotherapy to adults with depression in English (for example, this could be clinicians who primarily provide therapy to children, groups, diagnoses other than depression and/or conduct therapy in another language; or psychiatrists, nurses, nurse practitioners, case managers, other non-clinical staff) will engage in an abbreviated version of the battery of self-report measures which will include: (Appendix A): Demographic Questionnaire ([name] & Simons, 2011; Appendix A.1); Progress Monitoring Theory of Planned Behavior (Francis et al., 2004; Appendix A.2); Attitudes toward Standardized Assessment-Monitoring and Feedback (Jensen-Doss et al., *in press*; Appendix A.3); Monitoring and Feedback Attitudes Scale (Jensen-Doss et al., *in press*; Appendix A.4); Evidenced-Based Practices Attitudes Scale (Aarons, 2004; A.6); Sociometric Questionnaire (Valente et al., 2007; A.11); Opinion Leadership Scale (Childers, 1986). All questionnaires will be completed online using assessment software by emailing them a link or via hard copy (in-person). The questionnaires will take less than 30 minutes to complete and staff who complete the abbreviated baseline assessment will receive \$20 in compensation per assessment point. Note, from this point forward we will refer to this group of staff as the “general staff” to differentiate them from those completing the full baseline battery which we will refer to as simply “clinicians.”

Following the needs assessment, clinicians will be asked to participate in one four-hour training session that will introduce either the standardized MBC approach or the tailored MBC procedures. Clinicians will receive Continuing Education Units (i.e., education credit needed for licensure; maximum of four; to be determined) for attending the training. One training will be held at each site. The training will be scheduled such that all participating clinicians can attend and clinicians will receive productivity coverage credit for the four-hour training. In addition, immediately following the training a small battery of questionnaires will be administered to the clinicians to understand their training experience. This battery includes: Acceptability, Feasibility, Appropriateness for Training (Lyon, 2011, A.16-3); Post-Training Workshop EVALuation (TCU Institute of Behavioral Research, 2009; A.17); Clinical Teaching

Assessment Instrument (Litzelman, Stratogs, Marriot, & Skeff, 1998; A.18); Counselor Rating Form-Short (Corrigan & Schmidt, 1983; A.15), Progress Monitoring Theory of Planned Behavior (Francis et al., 2004; Appendix A.2); Attitudes toward Standardized Assessment-Monitoring and Feedback (Jensen-Doss et al., *in press*; Appendix A.3); Monitoring and Feedback Attitudes Scale (Jensen-Doss et al., *in press*; Appendix A.4); Perceptions of Adopting Measurement-Based Care (Moore & Benbasat, 1991; A.14) and Measure of Effective Attributes of Trainers (Boyd et al, unpublished; A.22). This will be completed by clinicians in-person following the training and will take about 20-25 minutes to complete. Clinicians will receive \$10 in compensation for completing the post-training battery.

In addition, one opinion leader and one self-nominated MBC champion (the opinion leader could also be the MBC champion, but in some cases this will be two different people) will be invited to participate on the implementation team based on the survey results from the needs assessment. The implementation team consists of research team members, site administrator, and 2-4 clinician opinion leader and champion, a client, and office professional. This team will convene for triweekly meetings during the 5-month active implementation phase and they are encouraged to meet without the researchers present during the 10-month follow-up period to facilitate identification of additional barriers (the number of actual meetings and attendance will be documented). Clinicians will be informed that consultation and training sessions will be audio-recorded for research team coding purposes, with the focus on capturing the barriers that emerged and the function of the discussions. Clinicians will be reminded at the beginning of each session not to use client names during consultation sessions to protect client confidentiality. Audio-recorded sessions will be transcribed using the procedures outlined for the focus groups. No clinician study participant identifying information will be retained in the transcripts and only 6-digit anonymous identification numbers will be used. The form found in Appendix B (MBC Barriers Coding Form; Appendix B.1) will be completed by implementation teams during their triweekly meetings; deidentified MBC Barriers Coding Forms will be analyzed for the purposes of research. Additionally, clinicians will have the option to complete the form found in Appendix B (MBC Consultation Form) prior to the triweekly meetings to facilitate consultation, the deidentified MBC Consultation Form form will also be analyzed for the purposes of research. Finally, a battery of surveys will be administered in-person and completed by those on the implementation teams at 5-months and 15-months during an implementation team meeting. These surveys include the Acceptability, Feasibility, Appropriateness for Implementation Teams and Conditions (Lyon, 2011; Appendix A.16-1, A.16-2); [name] Implementation Team Survey (A.19), and Edmondson Team Measure (Edmondson et al, 1999; A.20). These surveys will take about 25 minutes to complete and staff will receive \$15 in compensation per assessment point.

Clinicians have the option of entering and reviewing the PHQ-9 data with clients in the EHR. When they enter the data they should be given the option of answering additional questions about if/why they reviewed scores with client (see Appendix B.2). Due to technological issues with the EHR, not all clinicians currently have the option of completing these questions. To ameliorate this issue, clinicians at affected sites will have the option of filling out this information on paper each week (see Appendix B.4-1, B.4-2). This data will then be collected in person by CRI staff who will transfer it to a secure database. To offset the inconvenience of filling out a paper version of the questions and to encourage clinicians to do so, \$1 will be included with each paper survey.

At the end of the 5-month active implementation, clinicians will be asked to complete the same questionnaires in the above-listed baseline battery. Similar to the baseline battery of self-reports, these assessments will be completed online or via hard copy, and clinicians will receive \$50 per assessment battery completed. In addition, a subsample of clinicians at each site similar to at the beginning of Phase 2 will be asked to participate in a 1.5 hour focus group (Appendix E.1). Clinicians who participate in the focus group(s) will receive \$25 compensation. A subsample of clinicians at each site will also be invited to participate in individual exit interviews regarding their views about and use of the PHQ-9 (Appendix A.21). Clinicians who participate will receive \$20 compensation.

*10-month Post-Implementation/Sustainment.* Towards the end of the post-implementation/sustainment phase, another focus group with a subsample of clinicians from each site selected via purposeful sampling will occur (Appendix E.1). Similar to the focus group at the beginning of Phase 2 and end of Phase 2, participants will be compensated \$25. The same aforementioned baseline and 5-month active implementation assessment battery will be re-administered towards the end of the 10-month post-implementation/sustainment phase to assess factors influencing sustainment of MBC. Similar to the assessments before, clinicians will receive \$50 for completing the assessment.

The job category/title, licensure, supervisor information and demographics will also be obtained from the electronic health records at each site to obtain information about clinician experience. This information will be retrieved by a trained Centerstone Research employee who will be de-identify the information before providing it to the research team.

### **Clients: Across Both Conditions (i.e., Standardized and Tailored)**

#### **Phase 1 (Months 0-8)**

*Pre-Implementation.* A research assistant will contact potentially eligible clients via telephone and will perform an initial 10-20 minute phone screen to assess eligibility (RCR.3). A telephone version of the Patient Health Questionnaire-9 (PHQ-9; Appendix C.2) will be performed during the phone screening with the Centerstone Research Institute research assistant (CRI RA) in both conditions. This questionnaire should only take about five minutes to complete and clients will receive a \$5 incentive for completing the PHQ-9 regardless of their study eligibility. The client is deemed eligible if the client indicates that depression is a primary focus of treatment, s/he is seeking treatment with an enrolled study clinician, and s/he scores a 9 or higher on the PHQ-9. If the client is eligible, s/he will be asked to respond to a Client Demographics Questionnaire (Appendix C.1) over the phone during this initial screen. The data obtained from the initial PHQ-9 screen (RCR.3) and demographics questions is to be collected, labeled with a 9-digit anonymous research ID, and kept in a secure database in the secure server at Centerstone. If s/he is eligible and interested in participating, s/he will be asked to give verbal consent to participation over the phone during the initial screen conducted by the CRI RA. The CRI RA will also offer to call the client back if s/he would like time to review the informed consent statement before agreeing to participate. After a client verbally consents to participation or indicates that they would like time to review the consent statement, a

Welcome Packet, which will, contain the informed consent, authorization for the release of health information for research, and a stamped and return-addressed envelope will be sent to the client's address. The client will a \$5 gift card as compensation for PHQ-9 completion in the initial phone screen. If the client signs and returns the release of health information either via the pre-paid envelope or in person at their next session (additional information on the informed consent process can be found below in Section XII: Informed Consent Process), s/he is enrolled in the study. At this point the client will receive an additional \$5 compensation. If the client consents to research participation and the authorization for the release of health information for research, their verbal PHQ-9 and demographics data from the initial phone screen will be utilized as a baseline measure and be transported to IU for storage, given that the consent includes that the PHQ-9 completed for the eligibility screener and demographics questions can be used for the purposes of research. The 5-Axis diagnosis and employment, status, program activity involvement (i.e., type, start date, end date, care coordinator involved, face-to-face contact, location, reasons for discharge), date of first and last service, date of intake session, admission status (active/inactive), body mass index (BMI), age at BMI, demographics, medication use (i.e. prescription type, dosage, units, number of pills), and blood pressure (Appendix C.3) will also be retrieved from the clinician's intake report and health records to obtain information about comorbidities and functioning for all enrolled clients. This information will be retrieved by a trained Centerstone Research employee who will de-identify the information and then provide it to the research team.

## **Phase 2 (Months 8-38)**

*Client's Treatment (weeks 0-11).* Clients in the standardized condition will be asked to complete the hard copy PHQ-9 forms in the waiting room prior to every session with their enrolled study clinician, while clients in the tailored condition will complete the PHQ-9 according to the measurement-based care guidelines defined by the implementation team at each site. In all cases, clients will fill out the hard copy PHQ-9 prior to a session located in waiting room kiosks and completing the survey should only take about five to ten minutes. The client will then hand the completed PHQ-9 to his or her clinicians who will then enter it into the electronic health record so that the clinicians can review the PHQ-9 scores with the clients during the session. The CRI RA will pull the PHQ-9 data for all enrolled clients across the course of their treatment and provide it to the research team using the 9-digit anonymous identification number. In addition to the PHQ-9, clients will be asked to respond to a telephone or text message-based survey after each psychotherapy session to inquire as to whether their clinician discussed PHQ-9 scores in the session immediately preceding (Yes/No/NA) (Appendix C.4). Client can earn \$2 for every survey they complete for up to \$20. So clients may be able to earn an additional \$20 for completing these surveys after each session and the amount attained will be mailed with the \$10 incentive for completing the week 12 PHQ-9 (described below).

*Client's Treatment (week 12).* Clients will be reassessed for depression symptom severity via a phone interview (like the initial screen) at week 12 of their treatment, regardless of number of treatment sessions attended (Appendix C.2). A postcard reminder may be sent to clients before the phone interview as a reminder. The project coordinator and CRI RAs will track client time since entering treatment, beginning with the intake assessment. Clients will be mailed \$20 as an incentive for completing the week 12 assessment.

*Client's Treatment (week 13 and beyond).* Upon completion of the telephone assessment at week 12, PHQ-9 data collection for all enrolled clients will continue to occur according to the site guidelines for the duration of the study funding-period.

**Note.** In the unlikely case that an enrolled Centerstone client does not own a telephone, the research assistant will meet the client on-site for a hard copy version of the PHQ-9 in instances where a telephone version is supposed to be administered (e.g., for determining initial eligibility and in week 12). In addition, if a client does not have unlimited text messaging, we will offset the costs for the text message surveys by providing the client with \$5.

We will be asking permission to audiorecord client's therapy sessions for research purposes. These tapes would be reviewed and coded by an objective team of researchers trained in confidentiality to understand how measurement-based care is used in the community and to improve our understanding of how to help clients using measurement-based care. Only a subsample of client's audiotaped sessions would be reviewed and coded and these tapes will be randomly selected.

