## **C5. Leveraging Technology: Interfacing Tablet Data Collection with the Electronic Health Record**

NetSmart ([name] *Letter of Support*) has agreed to support the integration of the PHQ-9 into the electronic health record system and to work with our team to develop advanced features of the MBC

interface. Total score graphical displays showing session-by-session progress will be available to clinicians within the electronic health record and to clients on their personal health record via the tablet. Clinicians and clients will be able to view individual item-level information, with suicidality highlighted for careful review. Clinically significant change (5-point reduction), and lack thereof, will be flagged from session-to-session. The PHQ-9 will be available to clients on tablet kiosks in the waiting area for completion prior to session. In our pilot, clinicians indicated the importance of tablets as they: (1) felt clinician administration of the PHQ-9 was unnecessarily time-consuming, and (2) wanted to encourage clients to take ownership of symptom monitoring given the potential therapeutic benefits (Eisen, Dickey, & Sederer, 2000). Clients in our focus group unanimously requested private completion of the PHQ-9, indicating that this would promote comfort in sharing suicidality. Tablets are a cost-effective option that has been successfully used in similar protocols (Crits-Christoph et al., 2012). The technological and clinical innovations developed for this proposal present a generalizable protocol (documented in a manual) for widespread implementation given the proliferation of electronic health records. These technological enhancements will be made in both conditions during Phase I (months 0-8; see C11. Overview of Study Design).

[figure not shown]

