## C6. MBC Fidelity

In this proposal, fidelity to MBC is a three-level categorical variable defined by (a) client completion of the PHQ-9 (No=0, Yes=1), (b) clinician review of scores in the electronic health record (No=0, Yes=1), and (c) discussion of scores in session (No=0, Yes=1). The former two (PHQ-9 completion and clinician review of scores) will be automatically captured through the electronic health record. Clinicians will also check a box in the electronic health record progress note to indicate if they discussed scores in session, as this practice optimizes the effectiveness of MBC (Eisen, Dickey, & Sederer, 2000). Given the known limitations to clinician self-report, this latter fidelity criterion will also be assessed with client self-report via an automated telephone survey immediately after their session. In their first month of implementation, all clinicians (regardless of condition) will be asked to indicate factors they perceived to have limited MBC use. Through a drop-down menu embedded in the electronic health record progress note, clinicians will select contextual factors based on the literature (Dowrick et al., 2009; Garland, Kruse, & Aarons, 2003; Valenstein et al., 2009) and clinician-identified factors (from our pilot data); See Appendix for complete list of options (e.g. lack of time, client refused, clinician forgot).

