## **C10. Multifaceted Standardized and Tailored Implementation Conditions**

***Overview of the Blended Implementation Protocol.*** Both conditions (standardized and tailored) will employ the same blended protocol of implementation strategies to remove time and resource confounds (see Table 3). The guiding model (*Framework for Dissemination*; Figure 1; [name] et al., 2008), the best available literature on related efforts to promote MBC implementation (e.g., Evans & Hser, 2004; Harding et al., 2011; Lambert et al., 2005; Morris & Trivedi, 2011; Persons, Hong, & Koerner, 2012; Teruya, [name], Hser, & Evans, 2006), personal communication regarding program evaluation of a loosely tailored MBC implementation effort at Group Health clinics ([name], February 11, 2014), the MBC intervention framework, the partnership goals, and the pilot study defined the blended protocol of implementation strategies (Powell, McMillen, Proctor, et al., 2012). It was determined that embedding the PHQ-9 into the electronic health record was not sufficient but that using tablet computers would be essential to promote feasibility of implementation. The proposed local needs assessment is necessary to assess site-specific contextual factors and to identify opinion leaders and champions. In our pilot, we did not involve clinicians on the implementation team, but literature suggests this may be critical to achieving sustainment (Teruya, [name], Hser, & Evans, 2006) and it is consistent with our partnership goals. As such, each site will form an implementation team consisting of the PI, Co-I ([name]), the site administrator, a clinician identified as an opinion leader (via self-report; Childers, 1986), and a self-nominated MBC champion who will meet for at least 30 minutes prior to each triweekly consultation session. Training and consultation with experts are essential strategies for promoting clinician behavior change and fidelity to the intervention, particularly in the case of evidence-based psychosocial interventions (Herschell et al., 2010). A guideline will be set to specify the frequency of expected PHQ-9 administration with depressed clients. The order of strategies will proceed as follows within each site's 5-month active implementation period: (a) embed PHQ-9 in electronic health record; (b) conduct needs assessment; (c) form implementation team; (d) set guideline; (e) offer initial training; (d) conduct tri-weekly group consultation meetings (see C11. Overview of Study Design). In the 10 months post active imple-

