### III. Clinician Measures: Implementation Outcomes

MBC Fidelity	1. If clients complete the PHQ-9, it will be captured in the EHR (0=No, 1=Yes). 2. The EHR will reveal whether clinicians reviewed scores (0=No, 1=Yes). 3. Clinicians will self-report if they discussed scores in session (0=No, 1=Yes). Clients will respond via text to indicate whether clinician initiated score discussion in session. Reasons for MBC fidelity deviation will be captured via clinician report on progress notes.	BL, AT2, AT3
--------------	---	--------------

*Note* BL(AT1) = Baseline(Assessment Time 1), AT2 = Assessment Time 2, AT3 = Assessment Time 3.

**Retention.** The total time required for clinician study participation is 15 months; however, the first two assessments are obtained within the first 5 months. The average length of employment for a clinician at Centerstone is 6 years with an average of 11.72% attrition last year. We anticipate stable clinician participation for the granting period. Fortunately, literature suggests that participatory approaches to organizational change in practice patterns result in lower clinician attrition (Minkler & Salvatore, 2012). Even so, we will recruit 1.25 times more clinicians ( $N=187$ ) to accommodate attrition and achieve the target ( $N=150$ ). Because of the dynamic waitlist design, we will revisit enrollment in Phase 2, 3 months prior to each site's planned implementation. Finally, the design can handle attrition given the within- and between-subjects analyses and multiple assessment points (3 ATs), as can the analyses (multilevel modeling with multiple imputation, described below).

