**Data Collection.** The goal of client data collection is to determine if routine measurement (in the standardized condition) improves depressive symptom severity and whether adaptations to the MBC assessment schedule (tailored condition) have differential effects on depression outcomes. Clients will complete the PHQ-9 on a tablet kiosk in the waiting room according to site-generated guidelines; this information will be automatically fed into the electronic health record for clinicians to review in session. Given the potential for variable PHQ-9 completion in the tailored condition (based on the site-generated guideline), we will also have clients enrolled in both conditions complete the PHQ-9 at baseline (immediately post consent) and at week 12 of treatment (via automated phone survey). The 12-week window

reflects a commonly used time period in randomized clinical trials during which depressive symptoms are expected to remit. We will also supplement data collection with client 5-axis diagnoses and employment status captured in intake and progress review reports.

**Retention.** At recruitment, clients will complete a consent form and provide options for multiple contact methods (e.g. multiple phone numbers, address). Centerstone has consistently achieved greater than 75% client retention in federally-funded randomized trials (CATIE, Keefe et al., 2007; STAR\*D, Insel, 2006). We will replicate previous efforts to maximize retention in the proposed study. In order to have sufficient power to detect statistical significance and account for client attrition, we intend to recruit 1.25 more client participants ( $N=625$ ) to assure that we achieve our enrollment goal ( $N=500$ ).

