**Aim 1: Hypotheses:** Tailored implementation will outperform standardized in terms of (H1a) fidelity. MBC clinician fidelity was evaluated with two variables: (1) whether the PHQ-9 was recorded in the EHR, and (2) among encounters for which the PHQ-9 was recorded, whether it was discussed. Both outcomes were modeled using generalized linear mixed models with a logit link function for a binary distribution using the lme4 package. All models included random intercepts for clinicians and patients. Models for both outcomes were constructed in an identical sequence. Models comparisons in the model-building sequence described below were evaluated using the Bayesian Information Criterion (BIC); the model with the better BIC was selected for presentation. Several unconditional growth models (i.e., models with only parameters for time) were fit (i.e., linear, quadratic, log-transformed number of months). After establishing the unconditional growth model, additional fixed effects were added in the following sequence: (1) group main effect and (2) group x time interaction. Finally, new versus existing patient status was investigated as a main effect using a dummy variable for new patient status and as a patient status x group interaction.

**Aim 2: Hypotheses:** Contextual mediators will be leveraged in the tailored condition, but serve as barriers in the standardized condition. Mediation models were fit to evaluate which contextual factors (based on clinician-completed surveys, Table 5; and, clinician selection of drop-down menu reasons for MBC deviations captured in the electronic health record) mediate the impact of the implementation condition on both clinician- and client-level outcomes. The two critical effects underlying mediation were evaluated in separate models: treatment condition predicts the mediator (path *a*) and the mediator predicts the outcome (path *b*). Specifically, mediators were assessed at the conclusion of the implementation window and the mediators were used to predict PHQ9 completion in the sustainment window. The *a* path was assessed using linear mixed models with Satterthwaite degrees of freedom

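### The plan describes two incompatible PHQ-9 delivery routes; on the paper route the first H1a outcome measures completion plus clinician entry, not client completion

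*Combined protocol and SAP*

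**What the plan says.** **Tablet route.** C5 states: "The PHQ-9 will be available to clients on tablet kiosks in the waiting area for completion prior to session". C12b says of those scores that "this information will be automatically fed into the electronic health record for clinicians to review in session". The overview in section C, Table 3 and both condition descriptions in C10 say the same. C10 adds that "using tablet computers would be essential to promote feasibility of implementation".

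**Fidelity definition.** C6 defines component (a) as client completion and component (b) as clinician review, and states: "The former two (PHQ-9 completion and clinician review of scores) will be automatically captured through the electronic health record". Table 5, section III, agrees on (a): "If clients complete the PHQ-9, it will be captured in the EHR (0=No, 1=Yes".

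**Paper route.** Section VII (Clients, Phase 2, weeks 0–11) says that all clients, in both conditions, complete a hard copy before the session. It continues: "The client will then hand the completed PHQ-9 to his or her clinicians who will then enter it into the electronic health record". Section IX (Clients) also describes hard-copy forms in the waiting room. Section VII (Clinicians, Phase 2) treats entry as discretionary: "Clinicians have the option of entering and reviewing the PHQ-9 data with clients in the EHR".

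**Analysis.** C13a, Aim 1, makes the first H1a outcome "whether the PHQ-9 was recorded in the EHR". The second outcome is whether the score was discussed, analysed only in encounters that pass the first. C11 (Phase 3) says fidelity at tailored sites must be judged against each site's own guideline. C13a does not repeat this or give a denominator for the first outcome.

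**The concern.** H1a is half of the co-primary aim. On the tablet route, presence of a score in the EHR shows that the client completed the form. On the paper route it shows that the client completed the form and the clinician then chose to enter it. A reader of the H1a result cannot tell which of these was measured, or whether it was the same at all 12 sites. Because sites are the randomized units, a difference in route between sites would enter the comparison directly.

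The second outcome inherits the problem. An encounter in which a paper form was completed and discussed, but not entered, is excluded from the discussion analysis.

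**Working it through.** The plan gives no figure to reproduce here. The check sets the definitions side by side and then uses illustrative arithmetic.

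**1. What the first outcome measures.** Let c be the probability that a client completes a form that is due, and e the probability that the clinician enters a completed form.

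- Tablet route: P(recorded) = c. This matches component (a) in C6 and Table 5.
- Paper route: P(recorded) = c × e. This equals c only if e = 1, and Section VII makes entry optional.

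On paper, component (a) also overlaps component (b), because a clinician who types in the scores has seen them.

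**2. What the second outcome measures.** Let d1 be the probability of discussion when a completed form is entered, and d0 when it is not. Among completed forms, discussion occurs with probability e × d1 + (1 − e) × d0. The C13a outcome estimates d1 alone. The two agree only if e = 1 or d1 = d0.

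**3. Entry load by arm.** The standardized guideline is every session. The tailored examples in C10 are every other session and monthly. Assuming weekly sessions for 12 weeks and monthly as one session in four, the forms per client are:

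- every session: 12 × 1 = 12
- every other session: 12 × 0.5 = 6
- monthly: 12 × 0.25 = 3

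Every session is the maximum frequency, so the standardized load cannot be lower than a tailored site's. It is equal if a tailored site also chooses every session.

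**4. Possible effect on the contrast.** All completion and entry rates below are assumed. Completion is equal in the two arms. Forms-due rates are c × e; per-encounter tailored rates multiply this by 0.5 (every other session) or 0.25 (monthly).

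| c, both arms | e std | e tail | Std recorded | Tail, forms due | Tail, per encounter, every other session | Tail, per encounter, monthly |
|---|---|---|---|---|---|---|
| 90% | 60% | 60% | 54% | 54% | 27% | 13.5% |
| 90% | 60% | 90% | 54% | 81% | 40.5% | 20.25% |
| 80% | 80% | 90% | 64% | 72% | 36% | 18% |

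On forms due, the first two rows give a tailored-minus-standardized gap of 0 to 27 points with no difference in completion. The third row gives an odds ratio of (0.72/0.28)/(0.64/0.36) = 1.45. Exchanging the entry rates in the second row gives 54% − 81% = −27 points.

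Per encounter, the first two rows give gaps of −27 to −13.5 points (every other session) and −40.5 to −33.75 points (monthly). That reversal comes mainly from schedule frequency and would also occur on tablets: with e = 1 and c = 90%, every other session gives 0.5 × 90% = 45% against 90%. The denominator therefore has to be stated whichever route was used.

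**The case against.** Much of the case on the other side stands.

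- **Entry is clinician behaviour.** H1a is a clinician-level outcome, so a measure that includes entry is still informative. It is not what C6 and Table 5 call it.
- **Frequency is part of the randomized contrast.** If sparser schedules are better kept, that is a genuine consequence of tailoring, not an artefact.
- **Discussion has another source.** C6, Table 5 and Section VII describe a client report after each session, and C11 (Phase 3) plans to triangulate it with the clinician's. But C13a does not say that this report is used, and its condition on an EHR record excludes unentered forms regardless.
- **It is late to change data collection.** C13a is written in the past tense and reports that 22.8% of patients missed the 12-week interview. The paper that research staff collect under Section VII is the clinicians' answers about reviewing scores, not clients' PHQ-9 forms. With two research assistants covering distant sites (Section XII), a new collection of client forms would be neither cheap nor timely.

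Three stronger readings may tempt a reader; the documents support none of them:

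- **That the bias favours the tailored arm.** This needs lower entry in the standardized arm and a forms-due denominator. The first is unknown and the second is not stated in C13a.
- **That the pilot's 13.4% and 38.6% use shows the magnitude.** In C9 clinicians administered the PHQ-9 verbally, under a site-specific guideline, with EHR faults at one site. Paper entry was not tested.
- **That tablets are withheld from the arm that needs them most.** Section VII applies paper to both conditions.

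**Conclusion.** The contradiction is certain from the text and nothing resolves it. If paper was used, the first H1a outcome is completion and entry combined, the second is conditional on entry, and neither should be read as the fidelity component defined in C6. This follows from the definitions and needs no assumed rates.

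The size and direction of any bias are not established. They depend on entry rates that the documents do not give and on a denominator that C13a does not state. The 0 to 27 point range and the reversals show only that the contrast can move either way. Entry load is at least as high in the standardized arm, but that alone does not fix the direction.

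This should be fixed because it limits what the co-primary H1a result can conclude. Confidence is moderate.

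**What to change.** 1. Reconcile section C (overview), C5, C6, C10 with Table 3, and C12b with Sections VII and IX. State the delivery route by site and date.
2. Where paper was used, remove from C6 the statement that completion is captured automatically. Label the first outcome in C13a as *PHQ-9 completed and entered in the EHR by the clinician*, align the completion term used under Aim 2, and do not interpret the outcome as client completion.
3. State in C13a whether the denominator is forms due under the site guideline or all encounters.
4. Add a sensitivity analysis of discussion that does not condition on EHR entry, using the client survey already collected after sessions. Report its response rate by arm.
5. Score completion and entry separately only where paper forms were already retained. Do not require a new collection across the 12 sites.

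The cost is wording changes, one additional analysis of data in hand, and a narrower label for a co-primary outcome. No new data collection is needed.
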